#### Phase of Development: Phase II A

#### **Objectives:**

Primary Objective(s):

 To evaluate the safety of Sodium Nitrite infusion into the procured lungs and lung transplant recipient as reflected in blood mean arterial pressure and methemoglobin levels.

Secondary Objectives:

- To evaluate the efficacy of Sodium Nitrite infusion into the procured lungs and the lung transplant recipient in the prevention of grade 2-3 Primary Graft Dysfunction.
- To evaluate the efficacy of Sodium Nitrite infusion into the procured lungs and the lung transplant recipient in the prevention of delayed allograft complications including the incidence of acute rejection and BOS
- To identify the pharmacokinetic relationship of Sodium Nitrite and

metabolism of sodium nitrite in lung transplant recipients using blood sampling measures before and after drug exposure (will measure levels of plasma and whole blood nitrite, plasma nitrate, red cell iron-nitrosylhemoglobin, S-nitroso-hemoglobin and methemoglobin).

Statement of Primary Efficacy Hypothesis and Primary Analysis:

The administration of Sodium Nitrite at the time of organ procurement and transplantation will be safe and significantly reduce the rate of Primary Graft Dysfunction in patients undergoing lung transplantation.

**Planned Sample Size**: A total of 8 subjects will be enrolled into the protocol. Recruitment is expected to continue for six months.

Study Design: Phase IIA observational non-randomized cohort.

**Diagnosis and Key Patient Selection Criteria:** Males or females greater than 18 years of age or older undergoing lung transplantation.

**Treatments:** Sodium Nitrite infusion to the donor lungs and the lung transplant recipient.

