#### 2.4 Endpoints

#### Primary Endpoints Analysis

- The primary endpoint for the safety of Sodium Nitrite administration will be assessed by measurement of methemoglobin levels and mean arterial pressure during the nitrite infusion in the transplant recipient.
- The primary endpoint for the efficacy of Sodium Nitrite infusion will be the incidence of grades 2 and 3 PGD using the International Society for Heart and lung transplant (ISHLT) criteria for PGD based upon the worst value obtained over the initial 72 hours post lung reperfusion (T0-72).

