#### 3 Background and Rationale

While increasing numbers of patients with advanced lung disease are candidates for lung transplantation, the short- and long-term outcomes are severely compromised by graft dysfunction, primarily in the form of organ rejection. The earliest manifestation of lung allograft dysfunction, termed primary graft dysfunction (PGD), represents a form of ischemia-reperfusion acute lung injury, and occurs in its severest form (Grade 3) ranging from 10 to 35% of lung transplant recipients 1-6. PGD is the primary cause of early morbidity and mortality after transplantation and is strongly associated with the late development of chronic lung rejection or bronchiolitis obliterans syndrome (BOS) 7-9. Early graft dysfunction contributes significantly to the suboptimal outcomes of lung transplantation and to the failure of lung transplant recipients to achieve five-year survival rates comparable to patients who receive other solid organs such as the heart and liver. The risk of PGD further limits the time that lungs can be stored ex-vivo, therefore restricting the pool of available donors. A critical advance in the prevention of both early and late lung allograft dysfunction will occur if PGD can be successfully prevented or minimized.

The International Society for Heart and Lung Transplant (ISHLT) guidelines have provided a standardized definition for PGD based on the PaO2/FiO2 (P/F) ratio and the presence of chest radiograph infiltrates assessed within the first 72 hours following transplantation . The frequency of PGD has varied in published reports within the range of 70-80% as outlined in Table 1.

Table 1: Frequency of Reported PGD by Grade and Definition Using a Component of						
ISHLI Criteria						
Reference	Time (N)	Definition	PGD 0 (%)	PGD 1 (%)	PGD 2 (%)	PGD 3 (%)
Prekker 2005 (5)	1992-2004 (402)	T (0-48)		38%	28%	34%
Bobadilla 2008 (1)	1999-2008 (33)	Т72				30%
Daud * 2007 (7)	1998-2004 ( 334)	то	19%	39%	21%	21%

Table 1: Frequency of Reported PGD by Grade and Definition Using a Component of							
ISHLT Criteria							
Reference	Time (N)	Definition	PGD 0 (%)	PGD 1 (%)	PGD 2 (%)	PGD 3 (%)	
Huang * 2008 (3)	1998-2004 (334)	T48	17%	65%	8%	9%	
Christie 2009 (11)	2003-2007 (317)	Т24				20%	
Pittsburgh, unpublished	2003-2004 (76)	T (0-72)	21%	34%	20%	25%	

+ Grouped 0-1 into Group 1. Did not include radiographic scoring component

\* Identical cohort analyzed at different time points

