#### 5.9 Efficacy Assessment

The primary efficacy assessment will be the incidence of PGD Grade 3 or greater in comparison to age and disease-matched historical controls for the UPMC Lung Transplantation program.

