## 6 Statistical Consideration

Statistical analysis for the protocol will be primarily exploratory (i.e., hypothesis generating), and no firm conclusion will be drawn based upon a confirmation oriented statistical analysis. The results will be displayed as mean±standard deviation for continuous variables, or frequency (percentage), for discrete variables. For variables with skewed distributions, both nonparametric analysis, and parametric analysis using logarithmically transformed data will be performed. The continuous efficacy variables will be analyzed by analysis of variance (ANOVA) models, which will contain terms of treatment dose, disease type, and treatment-by-disease type interaction. The treatment-by-disease type interaction will be assessed at significance level 0.10. If the treatment-by-disease type interaction is not statistically significant, the interaction effect will be removed from the model. The treatment differences will be assessed by pair-wise comparison between the study population and historical controls, using least-square means from the ANOVA model. If baseline value of each continuous efficacy variable is to be adjusted, data will be analyzed by analysis of covariance (ANCOVA).

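### The historical controls for PGD have no source years, eligibility rule, number or lock date, so they can be chosen after the treated patients' grades are known

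*Combined protocol and SAP*

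**What the plan says.** The synopsis sets the size: "A total of 8 subjects will be enrolled into the protocol". Section 5.7.1 describes the study as non-randomized and, although its title mentions blinding, makes no provision for it.

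Section 5.9 defines the efficacy comparison: "The primary efficacy assessment will be the incidence of PGD Grade 3 or greater", set against "age and disease-matched historical controls for the UPMC Lung Transplantation program". Section 2.4 names a different event, saying that the efficacy endpoint "will be the incidence of grades 2 and 3 PGD", on the worst value over the first 72 hours.

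Section 6 mentions the controls once more. For continuous efficacy variables it plans a "pair-wise comparison between the study population and historical controls" based on ANOVA least-squares means. It gives no method for comparing a binary PGD rate.

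No section gives a calendar window, a source dataset, a number or ratio of controls, an age tolerance, eligibility criteria for controls, or a date by which the set is fixed. The only UPMC PGD figures are the row of Table 1 (Section 3) labelled "Pittsburgh, unpublished": 76 patients from 2003-2004, with 20% grade 2 and 25% grade 3 over 0 to 72 hours.

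Under Section 5.7.2, an independent committee grades the treated patients six to eight weeks after transplantation.

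**The concern.** With no concurrent arm, any efficacy signal is the gap between eight patients and a rate supplied by the control set. If that set is chosen after the eight grades are known, the analyst controls one side of the comparison, knowingly or not. Several choices of years, age tolerance and disease grouping would all satisfy the text of 5.9, and each could give a different rate.

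Matching on age and disease alone also leaves the two groups different in kind. Sections 7.1.2 and 7.1.4 exclude, among others, donors over 55 and recipients with pulmonary hypertension. Section 4.3.1 lists donor age and recipient pulmonary hypertension among the suggested risk factors for PGD. Controls who need not meet the trial's criteria would tend to be at higher risk, which favours nitrite.

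The result has a use. Sections 1 and 4 expect positive findings to lead to a larger trial.

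**Working it through.** **Plan's own figure.** The sample size of 8 comes with no effect size, power or alpha for PGD, so there is no calculation to reproduce.

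**Inputs.**
- Treated patients: n = 8 (synopsis).
- Reference rates from the Pittsburgh row of Table 1: p = 0.25 for grade 3 (the event in 5.9), and p = 0.20 + 0.25 = 0.45 for grades 2-3 (the event in 2.4). Table 1 gives this row as background, and it is used here only to set a scale.
- Number of controls m: not stated. Assumed range 8 (1:1) to 76 (the size of that row).
- Number of candidate control sets k: assumed 3 or 5, independent, with the same true rate.

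**Late choice.** The quantity is the mean of the largest of k values of Binomial(m, p)/m, from 200,000 simulations. With one set fixed in advance, the mean is p.

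| Set size m | p = 0.25, k = 3 | p = 0.25, k = 5 | p = 0.45, k = 3 | p = 0.45, k = 5 |
|---|---|---|---|---|
| 8 | 38.0% | 43.2% | 59.7% | 65.2% |
| 24 | 32.5% | 35.5% | 53.6% | 56.8% |
| 76 | 29.2% | 30.8% | 49.8% | 51.6% |

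With three sets of 8, the apparent benefit created by choice alone is 38 - 25 = 13 points for grade 3 and 60 - 45 = 15 points for grades 2-3. With sets of 76 it is about 4 and 5 points.

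**How far one small set can vary.** At a true 25%, the 2.5th to 97.5th percentile of the observed rate is 0% to 62.5% with 8 controls and about 16% to 36% with 76. A treated result of 0/8 gives a two-sided Fisher p of 0.47 against 2/8, 0.077 against 4/8 and 0.026 against 5/8.

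**Dependence on the reference rate.** Section 3 puts grade 3 PGD at "ranging from 10 to 35% of lung transplant recipients". If the drug does nothing, the chance of 0/8 is 0.90^8 = 0.43 at the lower end and 0.65^8 = 0.03 at the upper end.

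**Noise.** Under a common rate, ignoring matching correlation and differences between eras, SE of the difference = sqrt[p(1 - p)(1/8 + 1/m)]. For p = 0.25 and m = 8 this is sqrt(0.1875 x 0.25) = 0.217.

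| Controls m | SE, p = 0.25 | SE, p = 0.45 | Controls' share of variance |
|---|---|---|---|
| 8 | 0.217 | 0.249 | 50% |
| 24 | 0.177 | 0.203 | 25% |
| 32 | 0.171 | 0.197 | 20% |
| 76 | 0.161 | 0.185 | 9.5% |
| Fixed reference rate | 0.153 | 0.176 | 0% |

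Going from 8 to 32 controls cuts the SE by 1 - sqrt(0.15625/0.25) = 21%. The most that any number of controls can achieve is 1 - sqrt(0.125/0.25) = 29%. Even at that floor, the 95% half-width is 1.96 x 0.153 = 30 points for grade 3 and 1.96 x 0.176 = 34 points for grades 2-3.

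**The case against.** The strongest defence is one of weight. Safety is the primary objective and PGD prevention a secondary one (Section 2.3). Section 6 calls the analysis hypothesis generating and disclaims firm conclusions. With eight treated patients, no choice of controls makes the comparison precise. All of this stands, and it limits the harm. It does not remove the problem, because the decision to run a larger trial is tied to positive results.

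The radiology core and the grading committee are also independent of the patients' care. That protects the grading of treated patients. It does not govern who the controls are, and the plan does not say that either body would grade them.

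Four stronger readings are tempting but not supported:

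- **That a small 1:1 set is planned.** No ratio is stated, so the noise argument is conditional.
- **That a 13- or 15-point bias is to be expected.** Three independent sets of 8 is an assumption. Sets matched to the same eight patients within one programme would probably overlap and shift less.
- **That the 2003-2004 Pittsburgh cohort is the comparator.** Table 1 shows it as background, and neither 5.9 nor 6 names it.
- **That the spread of grade 2-3 rates in Table 1, from 17% to 62%, measures the analyst's freedom.** It mixes centres and time points. The 42% and 17% rows share one cohort, as the footnote says ("Identical cohort analyzed at different time points"). Section 5.9 limits controls to UPMC, and the 2.4 endpoint is the 72-hour worst value.

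**Conclusion.** The concern holds as a gap in the design. The source years, eligibility, number and lock date of the controls are all absent, and nothing stops them being settled after the treated grades are known. Writing the rule down afterwards would not restore the protection.

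The size can only be illustrated. Under the assumption of three independent sets of 8, the expected control rate moves from 25% to about 38% (grade 3) or from 45% to about 60% (grades 2-3). If 1:1 matching were used, the SE would be 0.217 or 0.249, against 0.171 or 0.197 with 32 controls, and a floor of 0.153 or 0.176 set by the treated group. Freedom of choice is the main problem. Extra noise is secondary and bounded. The plan should be changed, but the stated exploratory status keeps this from being critical.

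**What to change.** Before the first infusion, add a dated record to Section 5.9 or 6 that:

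- names the control source and one calendar window ending at trial start;
- restricts the pool to UPMC transplants whose recipients and donors meet Sections 7.1.2 to 7.1.4;
- fixes the matching rule (age tolerance and disease groups);
- uses either all eligible matches or a fixed ratio of several controls per patient.

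The matched list itself cannot be frozen at that point. Consent is taken at listing (Sections 5.3 and 7.2), so the eight recipients' ages and diagnoses are not yet known. Freezing the pool and the rule is enough, because the matches then follow mechanically.

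Grade the controls with the Section 5.7.2 criteria and the 72-hour worst-value rule as far as the records allow. Tabulate the Section 4.3.1 risk factors for both groups. State which PGD event is compared, since 2.4 and 5.9 differ.

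The cost is protocol wording and some chart abstraction, with no added patients. The drawback is a smaller pool for rare diagnoses. The comparison will still be exploratory and imprecise with eight treated patients.

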## 6 Statistical Consideration

Statistical analysis for the protocol will be primarily exploratory (i.e., hypothesis generating), and no firm conclusion will be drawn based upon a confirmation oriented statistical analysis. The results will be displayed as mean±standard deviation for continuous variables, or frequency (percentage), for discrete variables. For variables with skewed distributions, both nonparametric analysis, and parametric analysis using logarithmically transformed data will be performed. The continuous efficacy variables will be analyzed by analysis of variance (ANOVA) models, which will contain terms of treatment dose, disease type, and treatment-by-disease type interaction. The treatment-by-disease type interaction will be assessed at significance level 0.10. If the treatment-by-disease type interaction is not statistically significant, the interaction effect will be removed from the model. The treatment differences will be assessed by pair-wise comparison between the study population and historical controls, using least-square means from the ANOVA model. If baseline value of each continuous efficacy variable is to be adjusted, data will be analyzed by analysis of covariance (ANCOVA).

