#### 5.7 Study Procedures

#### 5.7.1 Randomization and blinding

This study will be a non-randomized pilot observational study.

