Plain film portable chest radiography will be obtained on D0 (within 6 hours of reperfusion), and D1, D2, and D3. All chest radiography will be referred to a radiology core for independent review and classification independent of the review required for clinical documentation.

Grade	PaO2/FiO2	Radiograph	
0	>300	Absent	
1	>300	Present	
2	200-300	Present	
3	<200	Present	

The primary end point of PGD will be scored using the following criteria:

The absence of pulmonary infiltrates on plain film radiograph will be assigned Grade 0 independent of the PaO2/FiO2 ratio. All extubated patients will be graded as 0 or 1 based upon the interpretation of the chest radiograph. The need for extracorporeal support and/or inhaled nitric oxide will be documented and automatically assigned a Grade III classification.

The diagnosis of Primary Graft Dysfunction (PGD) requires the exclusion of alternative conditions, which might produce a similar radiographic and physiologic pattern including hyperacute rejection, cardiogenic pulmonary edema, venous anastomotic obstruction, and allograft infection. Exclusion of these conditions will be made by a PGD grading committee composed of transplant physicians not involved in the patient's care at the time of transplant until hospital discharge. Medical records will be reviewed within six to eight weeks of transplantation by the committee to classify PGD.

• Sequential Organ Failure Assessment Score (SOFA):

The SOFA score is a recognized ICU scoring system to define the extent of the patient's organ failure. The scoring system has an individual component score for each of 6 organ systems including **respiratory**, **cardiovascular**, **hepatic**, **coagulation**, **renal** and **neurological** systems . The SOFA Score will be obtained daily at D1, D2, D3, and D4.

- Ventilator Free Days (VFD): Defined as the number of days off mechanical ventilationat 8am through D30 post transplantation.
- ICU Free Days (IFD): Defined as the number of days outside the ICU through D30 post transplantation.
- Hospital Days: Defined as the total number of acute and long term acute (LTAC) hospital days during the index transplant admission.

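### Section 6 gives the PGD incidence in 8 patients no measure of uncertainty and names no method for its promised comparison with historical controls

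*Combined protocol and SAP*

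**What the plan says.** The design is a single cohort: "A total of 8 subjects will be enrolled into the protocol", and "This study will be a non-randomized pilot observational study".

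Section 2.4 (Primary Endpoints Analysis) defines the primary efficacy endpoint as "the incidence of grades 2 and 3 PGD using the International Society for Heart and lung transplant (ISHLT) criteria", "based upon the worst value obtained over the initial 72 hours post lung reperfusion". Section 5.9 describes the primary efficacy assessment differently, as "the incidence of PGD Grade 3 or greater in comparison to age and disease-matched historical controls", and names no method. Section 5.7.2 scores PGD on an ordered scale of grades 0 to 3, introduced by "The primary end point of PGD will be scored using the following criteria".

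Section 6 is the whole statistical plan. Discrete variables are displayed as "or frequency (percentage), for discrete variables". For modelling, "The continuous efficacy variables will be analyzed by analysis of variance (ANOVA) models", and differences from historical controls are taken from the least-square means of that model. Skewed variables also get a nonparametric analysis and an analysis on the log scale. The section calls the analysis mainly exploratory and disclaims firm conclusions.

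**The concern.** Section 5.9 promises a comparison that Section 6, followed as written, cannot deliver. The ANOVA and ANCOVA are for continuous variables. The nonparametric provision is written for skewed variables that can also be log-transformed, which a grade scale starting at 0 cannot, and it does not mention PGD. No confidence interval, exact test, logistic model or ordinal model for PGD appears anywhere in the document.

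The report would then set one percentage from 8 patients beside a historical percentage. A result such as 12.5% against 45% looks like a large benefit, and nothing in the planned display would show that it is compatible with none. Sections 1 and 4 say that positive results should lead to a larger trial, so whoever designs that trial needs the uncertainty.

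**Working it through.** The document gives no precision or power calculation for the 8 patients, so there is no stated figure to reproduce.

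**Inputs**
- n = 8 (Synopsis).
- Illustrative reference: the unpublished Pittsburgh cohort in Table 1 (Section 3), n = 76, worst grade over 0-72 hours, grades 0/1/2/3 = 21/34/20/25%. Grade 2-3 is 20 + 25 = 45% (about 34/76); grade 3 is 25% (19/76).

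**Step 1. Exact interval for x/8.** The Clopper-Pearson limits are the 2.5% quantile of Beta(x, 9 − x) and the 97.5% quantile of Beta(x + 1, 8 − x). For x = 0 the lower limit is 0 and the upper limit is 1 − 0.025^(1/8) = 36.9%.

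| Observed | Percentage | Exact 95% CI |
|---|---|---|
| 0/8 | 0% | 0 to 36.9% |
| 1/8 | 12.5% | 0.3 to 52.7% |
| 2/8 | 25% | 3.2 to 65.1% |
| 3/8 | 37.5% | 8.5 to 75.5% |
| 4/8 | 50% | 15.7 to 84.3% |

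**Step 2. Grade 2-3 cut (Section 2.4).** Of the favourable results, only 0/8 excludes 45%.
- Binomial lower tails at 45%: P(0) = 0.55^8 = 0.0084; P(0 or 1) = 0.0084 + 8 × 0.45 × 0.55^7 = 0.063.
- Fisher's exact test against 34/76, two-sided: p = 0.019 for 0/8 and p = 0.13 for 1/8.
- The choice of interval does not drive this. The Wilson interval for 1/8 is 2.2% to 47.1%, which also includes 45%.

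**Step 3. Grade 3 cut (Section 5.9).** Even 0/8 does not exclude 25%: 0.75^8 = 0.100, and Fisher's test against 19/76 gives p = 0.19.

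**Step 4. Range over other reference rates.** The control rate is not given, so I took every series in Table 1.
- Grade 3 rates run from 9% to 34%. All lie below 36.9%, so 0/8 would exclude none of them.
- Grade 2-3 rates can be formed for four rows: 8 + 9 = 17%, 21 + 21 = 42%, 45%, and 28 + 34 = 62%. The interval for 1/8 includes the first three. It excludes 62%, which comes from a 402-patient series scored over 0-48 hours; the interval for 2/8 includes it.

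**Step 5. What the grade order would add.** Under proportional odds, information is proportional to 1 − Σp³.
- Four grades: 1 − (0.21³ + 0.34³ + 0.20³ + 0.25³) = 0.928.
- Grade 2-3 split: 1 − (0.55³ + 0.45³) = 0.7425. Ratio 0.928/0.7425 = 1.25.
- Separating only grade 0 from 1 in addition to that split: 1 − (0.21³ + 0.34³ + 0.45³) = 0.860, a gain of 16%.
- Separating only grade 2 from 3 in addition: 1 − (0.55³ + 0.20³ + 0.25³) = 0.810, a gain of 9%.

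Most of the 25% gain therefore comes from the grade 0/1 boundary. Under the Section 5.7.2 criteria that boundary rests on the radiograph alone.

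**The case against.** **The analysis is openly exploratory.** Efficacy is a secondary objective in the Synopsis, Section 6 disclaims firm conclusions, and anyone can compute an interval from x/8. This stands as a limit on the harm. It argues against confirmatory testing and not against showing uncertainty. The reader's own calculation also covers only the single proportion: the difference depends on the number of controls and how they are matched, which the document does not state.

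**The reference cohort is assumed.** The Pittsburgh series dates from 2003-2004, is unpublished and is not named as the control group. Sections 7.1.2 and 7.1.4 also exclude donors and recipients at higher risk. This stands; the 45% and 25% are illustrations. The intervals themselves do not depend on it.

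**A stronger reading is tempting.** A reader might infer that Section 6 throws away the grade order, and that an ordinal analysis should replace the incidence because it carries 25% more information. The documents do not support this.
- The dichotomy comes from the endpoint definitions in Sections 2.4 and 5.9. A frequency table under Section 6 could list all four grades.
- The gain assumes a roughly uniform shift, uses the same assumed cohort, and leans on the radiograph-only 0/1 boundary. Trial films go to an independent radiology core and PGD is classified by a committee; the document does not say that controls were read in this way.
- Simulated power for 8 against 76 at two-sided 0.05 is about 32% for Mann-Whitney and roughly 15% for Fisher on grade 2-3 at an assumed odds ratio of 0.35, and about 61% and 31% at 0.20. Part of that contrast is Fisher's conservatism, as its type I error is only about 2.4%. An uncorrected chi-square reaches roughly 20% and 38%.

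**Conclusion.** The concern holds as a gap in Section 6: no measure of uncertainty for PGD incidence and no method for the historical comparison in Section 5.9. At n = 8 the omitted interval is wide enough to change how a favourable result reads. Against an illustrative 45% grade 2-3 rate, 1/8 is compatible with no effect; against 25% grade 3, so is 0/8.

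The intervals assume only 8 evaluable patients with independent outcomes. The statements about compatibility also assume the Table 1 cohort as reference, and treat its rate as fixed except where Fisher's test is quoted.

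It should not be inferred that the trial would claim efficacy wrongly, since Section 6 disclaims firm conclusions, or that an ordinal analysis is required. An ordinal analysis is at most supportive. This is worth correcting but does not threaten the trial's safety objective.

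**What to change.** 1. Reconcile the PGD cut first: grades 2 and 3 in Section 2.4, grade 3 or greater in Section 5.9. No interval or comparison can be specified until one is named as primary.
2. In Section 6, report PGD incidence as x/8 with a Clopper-Pearson 95% confidence interval.
3. State how many historical controls there are, their period, and whether matching is individual or by frequency. Report the difference in incidence with an exact 95% confidence interval suited to that structure.
4. Show the full distribution of worst grade 0-3 over 0-72 hours for patients and controls.
5. As a supportive analysis only, and only if control grades exist for the same window, add an exact rank comparison of worst grade. Keep it unstratified or use coarse strata, because strata built on the age and disease match may hold one trial patient or none. State that it assumes a roughly uniform shift and depends on the grade 0/1 radiograph reading being comparable in controls.

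The cost is a short paragraph in Section 6 and a little programming. No new patient procedure is needed, since the grades are already collected. The control comparison does need patient-level control data, which Section 5.9 already implies. The downside is a wide interval that makes the result look less favourable, and one further exploratory analysis.

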## 5 Study Design and Methods

#### 5.1 Overview

This is a Phase IIA observational nonrandomized pilot investigation to evaluate the safety and efficacy of Sodium Nitrite administration for the reduction of PGD in patients undergoing lung transplant. The study will enroll 8 subjects, undergoing lung transplant at the University of Pittsburgh Medical Center (UPMC).

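### With 8 treated patients, the 0.10 interaction pre-test is a poor way to choose the ANOVA model for the continuous efficacy outcomes; a main-effects model should be fixed in advance (minor)

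*Combined protocol and SAP*

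**What the plan says.** Section 6 (Statistical Consideration) applies ANOVA to the continuous efficacy variables, with "terms of treatment dose, disease type, and treatment-by-disease type interaction". The decision rule is explicit: "The treatment-by-disease type interaction will be assessed at significance level 0.10", and "If the treatment-by-disease type interaction is not statistically significant, the interaction effect will be removed from the model". The estimate follows from whichever model survives: "The treatment differences will be assessed by pair-wise comparison between the study population and historical controls, using least-square means from the ANOVA model".

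The sample is fixed in the Synopsis ("A total of 8 subjects will be enrolled into the protocol") and again in Section 5.1. Section 5.7.1 confirms that there is no randomized comparator: "This study will be a non-randomized pilot observational study". Section 5.9 describes the historical controls as matched on age and disease, but gives no number or ratio. No section lists the disease types, pools rare ones or sets a minimum cell size. Sections 4.3.4 and 5.4 describe one recipient dose, 40 mg. Section 6 also calls the analysis primarily exploratory and disclaims firm conclusions.

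**The concern.** Eight treated patients spread over several diagnoses leave very small treatment-by-disease cells. An interaction test on such cells seldom detects a real interaction, yet still retains a spurious one about 10% of the time. Retention also changes what is estimated. Least-square means from the interaction model weight each disease equally, so a patient who is alone in a disease type counts as much as a whole cell. The interaction is most likely to look significant when that lone patient is extreme, and the same patient then drives the treatment difference. The estimate and its interval are therefore least reliable in exactly the trials where the rule selects the larger model.

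**Working it through.** **Inputs.** From the documents: 8 treated; pre-test level 0.10; removal if not significant; least-square-mean comparison with historical controls; disease matching (Section 5.9). Not in the documents, so assumed: 2 to 5 disease types; shares 40/35/25, 35/30/20/15 or 35/30/15/10/10; controls 1:1 (8) or 1:3 (24) in the same disease mix, with 76 as an upper value (the size of the local cohort in Table 1, which the plan does not name as the control group); SD = 1; final treatment test at two-sided 5%. The plan gives no power or effect size, so there is no figure of its own to reproduce.

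**1. Chance of a cell with exactly one treated patient.**
- Two equal types: 2 × 8 × (1/2)^8 = 16/256 = 6%.
- Three types (40/35/25): the single-cell terms 8p(1−p)^7 are 0.090 + 0.137 + 0.267 = 0.494. The three pairwise overlaps 56·p_i·p_j·p_k^6 sum to 0.032. Result: 0.462, or 46%.
- Four and five types, by the same multinomial: 74% and 84%.

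**2. Weight of a lone patient if the interaction is kept.** It is 1/k of the treated mean: 50%, 33%, 25% and 20% for k = 2, 3, 4 and 5, against about 1/8 = 12.5% otherwise.

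**3. Power of the pre-test for a 1 SD interaction.** For disease j with t_j treated and c_j controls, let w_j = t_j·c_j/(t_j + c_j) and W = Σw_j. If disease j's treatment effect differs from the rest by δ, the noncentrality is λ = δ²·w_j(1 − w_j/W), on k−1 and n−2k degrees of freedom. In the first three rows the disease that differs is the one with the lone patient.

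| Treated layout | Controls | λ | df | Power at 0.10 |
|---|---|---|---|---|
| 1/1/1/2/3 | 8 | 0.5 × (1 − 0.5/4) = 0.44 | 4, 6 | 12% |
| 1/7 | 8 | 0.5 × (1 − 0.5/4) = 0.44 | 1, 12 | 17% |
| 1/7 | 24 | 0.75 × (1 − 0.75/6) = 0.66 | 1, 28 | 20% |
| 4/4 | 8 | 2 × (1 − 2/4) = 1.0 | 1, 12 | 25% |
| 4/4 | 24 | 3 × (1 − 3/6) = 1.5 | 1, 28 | 33% |

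The layouts 1/3/4, 1/1/6, 1/1/2/4 and 1/1/1/5 fall inside 12-20%. If a better-filled disease is the one that differs, power is somewhat higher: in 1/3/4 with 24 controls and the four-patient disease differing, λ = 3 × (1 − 3/6) = 1.5 on 2 and 26 df, about 26%. With 76 controls, 1/7 reaches 23% and 4/4 reaches 38%.

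**4. SE of the treatment difference (SD units).** Additive model: 1/√W. Interaction model: (1/k)√Σ(1/w_j). With 8 controls the additive SE is 1/√4 = 0.500.
- 1/7: ½√(2 + 0.286) = 0.756, 51% larger.
- 1/3/4: ⅓√(2 + 0.667 + 0.5) = 0.593, 19% larger.
- 1/1/1/2/3: ⅕√(2 + 2 + 2 + 1 + 0.667) = 0.554, 11% larger.

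The ratios are the same with 1:3 matching. A flatter split pays less: 1/1/2/2/2 gives ⅕√7 = 0.529, or 6%.

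**5. Error rate of the whole procedure under no treatment effect and no interaction (simulation).**

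| Layout; controls | Interaction kept | Rejects when kept | Overall | Additive model |
|---|---|---|---|---|
| 4/4; 38/38 | 9.8% | 6.2% | 5.2% | 5.1% |
| 1/3/4; 10/28/38 | 9.4% | 13.4% | 6.0% | 5.2% |
| 1/1/2/4; 3/3/6/12 | 10.0% | 12.2% | 5.9% | 5.2% |
| 1/7; 1/7 | 10.1% | 30% | 7.4% | 4.8% |

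Across the single-patient layouts the ranges are about 11-31% when the interaction is kept and about 5.3-7.6% overall. The additive model holds 5% up to simulation error. In the 1/3/4 row the interaction-model SE is 0.440, but the estimates spread with SD 0.563 in the trials that kept the term. This is why the nominal interval is too short there.

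**The case against.** The best defence is about size and scope, and much of it stands. Section 6 declares the analysis exploratory. The ANOVA covers continuous variables such as oxygenation-index AUC and ventilator-free days, which Section 2.4 lists as secondary. PGD incidence is binary and outside this model, as are the MAP and methemoglobin safety endpoints. Overall error rises by only about 0.3 to 2.6 percentage points. Every magnitude depends on a disease mix and a control number that the plan does not give.

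Four stronger readings are tempting, and the documents do not support them:
- *The model will often be non-estimable.* Under the assumed shares the treated group misses at least one disease type in about 15%, 48% and 83% of trials (3, 4, 5 types). That leaves an empty cell only if the controls include a disease that no treated patient has. With disease-matched controls, as Section 5.9 describes, that disease drops out of the model.
- *The pre-test is powerless whatever happens.* With two equal cells of four and 76 controls, power is 85% for a 2 SD interaction.
- *A lone patient always carries at least a quarter of the estimate.* With five types it is a fifth of the treated mean.
- *The dose term is confounded with hemodynamic instability.* That would need the term to mean dose received, which could vary through the infusion holds in Section 5.6. The plan nowhere defines it so. Section 6 itself compares the study population with historical controls, so the natural reading is treatment group. What remains is a label that does not fit a single planned dose, and it does not cause the small-cell problem.

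The exploratory label does not dispose of the point. It limits what may be claimed, but it does not correct an interval that is too short in the trials that keep the interaction.

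**Conclusion.** The concern holds as a minor one. The rule in Section 6 selects the model with a weak test and, when it selects the interaction, lets single patients dominate the treatment estimate. With a single-patient cell and 1:1 or 1:3 matched controls, power for a 1 SD interaction is about 12-20% (25-33% in a 4/4 split). In the layouts examined the SE is about 11-51% larger if the term is kept. The treatment test rejects about 11-31% of the time in the roughly one null trial in ten that keeps it. Overall error is about 5.3-7.6% against 5%. These figures rest on the assumed disease shares, matching ratios and interaction size; with two evenly represented disease types the problem would be uncommon. A reader might infer that the trial's main conclusions are at risk. They are not, because neither PGD incidence nor safety passes through this model.

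**What to change.** In Section 6, prespecify one model for the continuous efficacy variables: treatment group (nitrite versus historical control) plus disease type, both as main effects, with rare diseases pooled by a rule written before the data are seen. Delete the interaction test and its removal rule, and present disease-specific results descriptively. As a wording correction, replace *treatment dose* with *treatment group*, since only one recipient dose is planned.

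The cost is a change of text only. What is lost is a formal interaction test, which has little power with 8 treated patients. Disease type stays in the model, which is sensible because Section 4.3.1 names recipient diagnosis as a possible risk factor for PGD.
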